4.10.2 Adverse Events of Interest

For this study the adverse events of interest are:

4.10.2.1 Elevated Liver Function Tests (LFTs)

- Alanine aminotransferase (ALT) Grade ≥ 3 (>5.0 x upper limit of normal (ULN))
- Aspartate aminotransferase (AST) Grade ≥ 3 (>5.0 x ULN)
- Bilirubin Grade ≥ 3 (>3.0 x ULN)
- Alkaline phosphatase (ALP) Grade ≥ 3 (>5.0 x ULN)
- ALT or AST >3.0 x ULN **WITH** Bilirubin >2.0 x ULN

4.10.2.2 Hepatic Adverse Events

- All hepatic AEs

All hepatic AEs and liver function test (LFT) abnormalities will be reviewed by an Independent Hepatic Expert Committee, at least quarterly, and as needed. Tabulation for AEs of interest will be provided.

Hemorrhagic events, Infection events, and Infusion related reaction events may be included in the scope of the AEs of interest depending on the study safety profile.

4.10.3 Clinical Laboratory Evaluation

In general, laboratory data of hematology and clinical chemistry after the first subsequent anti-cancer therapy, if any, will be excluded in summary due to confounding effect of the therapy.

Summary statistics (N, mean, SD, median, and range) will be calculated for the raw data and for their changes from baseline by scheduled visits, as well as for last value and for the changes from baseline to the last value. Within a cycle, summary statistics of the worst values will be provided. Individual values outside the normal ranges will be identified (by “H” for high and “L” for low) in the data listings displaying the absolute values for each subject.

Displays of over-time summaries will be presented for the following key laboratory parameters: hemoglobin, platelet count, white blood cell count, absolute neutrophil count (ANC), international normalized ratio (INR) (or prothrombin time) and activated partial thromboplastin time (aPTT), sodium, potassium, blood urea nitrogen, creatinine, total bilirubin (with fractionation if abnormal), ALT, AST, ALP, lactate dehydrogenase, and albumin.

Shift tables for each cycle will be produced for selected laboratory parameters, including hemoglobin, platelet count, white blood cell count, ANC, total bilirubin, ALT, AST, and ALP. These tables will summarize by cycle the number of subjects with each baseline CTCAE grade and changes to the maximum CTCAE grade in the cycle. For laboratory parameters without CTCAE grade, shifts from baseline to highest (Low, Normal, High) categories per cycle will be used.

Shift tables from baseline to worst value on treatment (from treatment start to 30 days after last dose or the end of treatment visit date, whichever is later) will also be provided. The worst toxicity grade during the study will be tabulated.

In addition, incidence of persistent (≥ 4 weeks) and severe (grade 3 or higher) cytopenia (thrombocytopenia/neutropenia) and LFT will be evaluated. Time to onset and duration of grade 3 or 4 thrombocytopenia/neutropenia and LFT will be summarized.

4.10.4 Vital Signs, Physical Examination Findings and Other Safety Observations

Over-time summary statistics (n, mean, SD, median and range) of vital signs (temperature, pulse/heart rate, systolic blood pressure and diastolic blood pressure) will be provided for each scheduled visit. A separate summary will be produced for vital signs at baseline, maximum, minimum, change to maximum, change to minimum, last value, and change to last value.

Abnormal baseline physical examination findings will be summarized with the medical history. New or worsened physical examination abnormalities will be analyzed as AEs.

Baseline ECG data will be summarized.

4.10.5 Safety Monitoring: Data Monitoring Committee (DMC) and Independent Hepatic Expert Committee (HEC)

For Part 1 of the study, the DMC performed ad hoc expedited reviews of any \geq Grade 4 hemorrhagic event occurring on the study or any other safety concerns identified by the sponsor.

The first planned DMC safety review meeting for Part 2 of the study will be held after approximately 60 subjects (~30% of the expected enrollment) have been randomized, and subsequent safety review meetings are planned approximately every 6 months thereafter and hold ad hoc meetings if required. The DMC will review unblinded reports for safety as well as efficacy to evaluate risk versus benefit when possible. The summary reports on enrollment, demographic data and baseline characteristics, and conduct of the study will also be reviewed. Separate unblinded biostatistician and programmer team will support the DMC in Part 2.

Data to be reviewed by the DMC periodically are specified in the DMC SAP, which is specifically prepared for DMC reviews.

All hepatic AEs and LFT abnormalities will be reviewed by an Independent Hepatic Expert Committee (HEC), at least quarterly, or as needed. Full details of the DMC and HEC procedures and processes can be found in the DMC Charter and HEC Charter.

4.11 Other Analyses

4.11.1 Study impacts due to COVID-19 pandemic

Protocol Amendment 4 is issued in consideration of the COVID-19 pandemic. The following data will be summarized as appropriate for all subjects and by treatment group to evaluate the impacts on study due to the COVID-19 pandemic. By-subject listings will be provided as well.

4.11.1.1 Evaluation of the COVID-19 impacts on efficacy endpoints

- Impacts of delayed or reduced transfusions on 8-week, 24-week TI, time to and duration of TI, HI-E (transfusion reduction):
 - Intended transfusion types, intended transfusion units if reduced, the indications of transfusion, and reasons of delay along will be summarized and listed.
 - Number and percentage of subjects with delayed or reduced transfusions.
- Impacts of delayed/missed visit and assessment on other key secondary endpoints, e.g. HI-E (Hb), disease response, PFS, and time to AML
 - incidence will be summarized by parameter and listed.

4.11.1.2 Evaluation of the COVID-19 impacts on safety endpoints

- Death and treatment discontinuation will be summarized and listed.
- TEAEs related to COVID-19 will be summarized and listed similarly as other TEAEs.
- Delayed/missed lab will be summarized by lab parameter and listed.
- Delayed cycle/dose will be summarized and listed.

4.11.2 Pharmacokinetics/Pharmacodynamics (PK/PD)

Included in the secondary objectives of this study is to characterize PK of imetelstat in study subjects. Specifically, individual-specific PK parameters will be estimated based on observed imetelstat concentrations and a previously established population PK model. Included in the exploratory objectives of this study is to evaluate potential relationship between imetelstat exposure (e.g., C_{max} and AUC) and clinical efficacy, safety/hematology, and biomarker endpoints.

Separate analysis plan document will be provided by the PK/PD analysis group and details will be provided in a separate report with analysis results.

4.11.3 Ventricular Repolarization substudy (Part 2)

Additional ECG analysis and exposure-response analysis for the Ventricular Repolarization substudy in Part 2 will be provided in the Ventricular Repolarization Substudy Cardiac SAP and will be performed separately from the primary analysis of 170 subjects in the main study of Part 2. Safety data and available data from efficacy will be summarized based on the main study SAP.

4.11.4 Medical Resource Utilization (Part 2)

The effect of treatment on medical resource utilization is listed as the secondary objective. Medical resource utilization data, associated with medical encounters, will be collected in the eCRF in Part 2 by the investigator and study-site personnel for all subjects throughout the study including the long-term follow up after termination of treatment. Protocol-mandated procedures, tests, and encounters are excluded. The data collected will be used to conduct the health economic analyses and will include:

- Frequency and duration of hospitalization (total days length of stay, including duration by wards; e.g. intensive care unit)
- Outpatient medical encounters and treatments (including physician or emergency room visits, selected tests and procedures, and medications)

Frequency and duration of hospitalization, frequency of emergency room visit and specialty physician visit will be listed and summarized where appropriate. Results may be grouped by treatment, subgroups, or clinical response.

Medical resource utilization data collection is not required for subjects participating in the Ventricular Repolarization substudy (after Protocol Amendment 7).

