Synopsis (Overview of Study Design), Section 3.1 (Overview of Study Design), Section 9.1.6 (Extension Phase), Section 11.12 (Independent Hepatic Expert Committee)	Added text to clarify that Hepatic Expert Committee review of AEs and LFT abnormalities will continue in the Extension Phase.
Section 2.1 (Objectives)	Added primary objective for the Extension Phase evaluating the long-term safety, OS, and disease progression, including progression to AML in transfusion dependent subjects with low or intermediate-1 risk MDS that is relapsed/refractory to ESA treatment receiving imetelstat.
Section 3.1 (Overview of Study Design-Schematic)	Added Figure 3 depicting Extension Phase
Section 3.2 (Study Design Rationale), Section 5.2 (Blinding)	
 Clarified study blinding and added 'Unblinding' to section title. Added text to clarify that subjects, investigators, and study team members will be unblinded after primary efficacy analysis.
Section 3.3 (Rationale for the Extension Phase)	Section added to describe rationale for adding Extension Phase
Synopsis (Dosage and Administration), Section 6 (Dosage and Administration), Section 7 (Treatment Compliance)	Text regarding guidelines for drug administration and dose modification in Extension Phase was added
Section 7 (Treatment Compliance)	Text that the guidelines for study drug administration and data collection continue in the Extension Phase
Section 8.3 (Concomitant Medication)	Text that recommendations for concomitant therapy continues in the Extension Phase
Section 9.1.1 (Overview)	
 Text was added with Amendment 8 to add the Extension Phase Blood volume table for Extension Phase added
Section 9.1.6 (Extension Phase)	Section added explaining Extension Phase procedures
Table 3 (Time and Events for Part 2 Main Study); Section 9.7 (Medical Resource Utilization)	Duration of collection of medical resource utilization data was updated to start from time of first dose and end at the End of Treatment visit. As the analysis will focus on the treatment emergent MRU, the duration of data collection has been changed from ending at start of subsequent therapy to end at EOT or 30 days after the last dose of study drug, whichever occurs later.

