- BM aspirate, biopsy: Clarified text regarding requirements for BM assessment. Updated to no longer require in Posttreatment Follow-up
- Response assessment: Updated to specify that assessment is only required at time of suspected PD in Posttreatment Follow-up. Included text to specify that CR, PR or mCR only to be assessed in subjects with >5% baseline bone marrow aspirate blasts.
- INR (or PT) and aPTT (local laboratory): Modified assessment schedule because clinically significant changes to coagulation laboratory parameters in imetelstat treated subjects have not been found in Part 1 and in other recent studies. Schedule modified to require assessments at Cycle 1 Day 1 and repeat during study if subject has a Grade ≥ 3 bleeding event (instead of at each cycle).
- BM aspirate for cytogenetics (central laboratory): Clarified text regarding requirements for cytogenetic assessments.
- BM aspirate for RNA Seq or CyTOF (if feasible); Mutation Analysis: The timing of the assessment was clarified to include RNA Seq or Cytof at the time of mCR was added.
- Text was added to state that the following assessments in post-treatment follow-up will only be required until the start of subsequent therapy: MRU, FACT-An, EQ-5D-5L, QUALMS, PGIC

Table 4: Time and Events for Part 2, Main Study Pharmacokinetic / Immunogenicity Sampling	
The following updates were included:
 
 • Table Title was updated to specify it is applicable to the Main Study of Part 2. • Footnote edited to remove Ventricular Repolarization study (QTc) substudy language.
Section 2.1 (Objectives)	For Secondary Objectives add clarifying text for the Qtc interval objective to state it will be reported separately from Part 2.
Section 3.1 (Overview of Study Design); Figure 2: Schematic Overview of the Study Section 5.2 (Blinding)	Updated text and figure to reflect modified Ventricular Repolarization substudy and to reflect clarification for required assessments as per Time and Events Table.
Section 4.1 (Inclusion Criteria)	
The following updates were included:
 
 • Inclusion Criteria no. 8.1 removed the text “(ie, $\geq 1500/\text{mm}^3$)” • Inclusion Criteria no. 8.2 removed the text “(ie, $\geq 75,000/\text{mm}^3$)”

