Concomitant therapy			X	Continuous				X	
Adverse events			X	Continuous				X	
Medical Resource Utilization	Data associated with medical encounters (not protocol specified), will be collected for all subjects throughout the study from the time of first dose until the EOT or 30 days after the last dose of study drug, whichever occurs later.			Continuous				X	
Abbreviations: AML = acute myeloid leukemia; BM=Bone Marrow; C=Cycle; CR=complete remission; CyTOF=cytometry by time of flight ; D=Day; DBP=diastolic blood pressure; EOT=end of treatment; EPO=erythropoietin; EQ-5D-5L=EuroQol-EQ-5D-5L; FACT-An= Functional Assessment of Cancer Therapy - Anemia-Related Effects; HI-E (Hb)=hematologic improvement-erythroid (hemoglobin); HR=heart rate; GGT= gamma-glutamyl transpeptidase; hTERT = human telomerase reverse transcriptase; INR=international normalized ratio; IRR=infusion-related reaction; IWRS=interactive web response system; mCR=marrow complete remission; MDS = myelodysplastic syndrome; PD=disease progression; PE=physical exam; PGIC= Patient Global Impression of Change; PK=pharmacokinetic; PR=partial remission; PT=prothrombin time; QUALMS= Quality of Life in Myelodysplasia Scale; SBP=systolic blood pressure; TA=telomerase activity; TL=telomere length; ULN=upper limit of normal									

Table 4: Time and Events for Part 2, Main Study Pharmacokinetic / Immunogenicity Sampling

Study Day	Pharmacokinetic Blood Sampling Time ^a	Pharmacokinetic Blood Sampling	Immunogenicity Evaluation
Cycle 1 Day 1	0 (before start of infusion)		X
Cycle 1 Day 1	2h ^b (end of infusion)	X	
Cycle 1 Day 1	4-5 h	X	
Cycle 1 Day 1	6-7 h	X	
Day 1 of all subsequent cycles	2h ^b (end of infusion)	X	
Day 1 of Cycles 4, 7, 10, etc.	0 (before the start of the infusion)		X
If IRR is observed	As soon as possible after IRR is observed	X	X ^c
End of Treatment	During the visit		X
First Posttreatment Follow-up, if feasible	During the first visit		X

- a. All samples are collected at the time point relative to the START of the infusion.
- b. For the 2-hour time points (relative to the start of the infusion), the pharmacokinetic sample should be taken immediately before the end of the infusion (ie, this includes cases where infusion time is extended beyond 2 hours).
- c. An aliquot from the pharmacokinetic sample will be used to assess immunogenicity (separate blood draw not needed).

Table 5 Time and Events Schedule for Extension Phase

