9.7. Medical Resource Utilization (Part 2 Only)

Medical resource utilization data, associated with medical encounters, will be collected in the eCRF in Part 2 by the investigator and study-site personnel for all subjects throughout the study from the time of first dose until EOT visit or 30 days after the last dose of study drug, whichever occurs later. Medical resource utilization data collection is not required for subjects participating in the Ventricular Repolarization substudy (after Protocol Amendment 7).

Protocol-mandated procedures, tests, and encounters are excluded. The data collected may be used to conduct exploratory economic analyses and will include:

- Frequency and duration of hospitalization (total days length of stay, including duration by wards; eg, intensive care unit)
- Outpatient medical encounters and treatments (including physician or emergency room visits, selected tests and procedures, and medications)

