1 INTRODUCTION

This study is designed to evaluate the efficacy and safety of imetelstat in transfusion-dependent subjects with low or intermediate-1 risk myelodysplastic syndrome (MDS) that is relapsed / refractory to erythropoiesis-stimulating agent (ESA) Treatment.

The purpose of the statistical analysis plan (SAP) is to lay out key elements including definitions and statistical methods for the planned analyses for the primary, secondary and exploratory endpoints. It describes the final reporting for study MDS3001 as per protocol amendment #7 dated as September 2, 2021. Safety data to be reviewed by the Data Monitoring Committee (DMC) periodically are specified in the DMC SAP, which is specifically prepared for DMC reviews.

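### SAP 4.11.4 describes a collection period for medical resource use that the protocol no longer has, and neither document sets an analysis cut-off or a person-time denominator, so counts can cover unequal observation time.

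*SAP*

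**What the plan says.** **SAP.** Section 4.11.4 says medical resource use will be collected in Part 2 "for all subjects throughout the study including the long-term follow up after termination of treatment". It says these data will feed health economic analyses. It plans listings and summaries of the frequency and duration of hospitalization and the frequency of emergency and specialist visits, which may be grouped by treatment, subgroup or clinical response. It gives no cut-off date and no denominator. Section 3.2.2 lists medical resource use as a secondary endpoint. The SAP introduction fixes the protocol version it follows: "It describes the final reporting for study MDS3001 as per protocol amendment #7 dated as September 2, 2021". SAP version 2.0 is dated 15 September 2022.

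**Protocol.** The current version is Amendment 8, dated 13 December 2022. Section 9.7 collects these data "from the time of first dose until EOT visit or 30 days after the last dose of study drug, whichever occurs later", and the matching row of Table 3 agrees: "from the time of first dose until the EOT or 30 days after the last dose of study drug, whichever occurs later". Section 11.9 plans the same kinds of summary as the SAP, again with no window and no denominator.

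**History, from the amendment log.** Under Amendment 7, several post-treatment assessments, resource use among them, "will only be required until the start of subsequent therapy: MRU, FACT-An, EQ-5D-5L, QUALMS, PGIC". Amendment 8 then shortened the period: "the duration of data collection has been changed from ending at start of subsequent therapy to end at EOT", with the 30-day post-dose point applying instead where it falls later. It gave the reason: "As the analysis will focus on the treatment emergent MRU".

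**The concern.** The two current documents give different periods for the same secondary endpoint, and a programmer working from the SAP would find only the longer one. The mismatch would be a matter of wording if an analysis rule sat on top of it, but none does.

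A raw count of hospitalizations depends on how long the subject was observed. Here that time can vary for reasons other than need for care:

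- A subject who stopped treatment before Amendment 8 may have post-treatment encounters on file. A subject who stops later will not.
- Treatment runs until progression, unacceptable toxicity or withdrawal of consent, so even the protocol's own window differs in length between subjects and depends on outcome.
- Protocol 3.2 allows imetelstat subjects to continue after the primary analysis is unblinded, while placebo subjects may stop and enter follow-up. By the final analysis of the main study, 24 months after the last randomization, observation time may therefore differ by arm.

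At stake is how far the by-arm summaries, and any economic model built on them, can be interpreted.

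**Working it through.** The documents give no rate, event count or precision for medical resource use, so there is no stated figure to reproduce. The check is a comparison of texts, followed by an illustration.

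**Step 1. The periods side by side.**

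| Source | Collection ends |
|---|---|
| SAP 4.11.4 (v2.0, 15 Sep 2022) | Runs through long-term follow-up |
| Amendment 7 rule (log, history only) | Start of subsequent therapy |
| Protocol 9.7 and Table 3 (Amendment 8) | Later of EOT visit and last dose + 30 days |
| Analysis cut-off in SAP 4.11.4 or protocol 11.9 | None stated |

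The SAP wording therefore differs from the current protocol, and it also omits the stop at subsequent therapy recorded for Amendment 7.

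**Step 2. Length of the protocol window.** With 28-day cycles and no delays, the time from first dose to last dose + 30 days is 28 × (cycles − 1) + 1 + 30 days.

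- 8 cycles (median in the Part 1 target population, protocol 1.1.5): 28 × 7 + 31 = 227 days.
- 12 cycles (median assumed for blood volumes, footnote to protocol Table 12): 28 × 11 + 31 = 339 days.

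Neither figure is a Part 2 duration by arm. They serve only as plausible lengths.

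**Step 3. One common window, raw counts.** At the same event rate in both arms, the expected count is proportional to days observed. Arms averaging 12 and 8 cycles give 339/227 = 1.49. Aligning the window does not remove this; dividing by person-time does.

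**Step 4. Mixed windows, raw counts.** Assume a share f of each arm is counted to 730 days and the rest to last dose + 30 days. The mean window is f × 730 + (1 − f) × treatment window. The 730 days is an assumption: subjects randomized early could be followed longer, and the Amendment 7 rule would often have stopped sooner.

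| Imetelstat | Placebo | Mean days | Ratio of counts at equal rates |
|---|---|---|---|
| 8 cycles, f = 0.5 | 8 cycles, f = 0.5 | 478 vs 478 | 1.00 |
| 12 cycles, f = 0.5 | 8 cycles, f = 0.5 | 534 vs 478 | 1.12 |
| 12 cycles, f = 0.3 | 8 cycles, f = 0.7 | 456 vs 579 | 0.79 |
| 8 cycles, f = 0.7 | 12 cycles, f = 0.3 | 579 vs 456 | 1.27 |

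The ratio falls on either side of 1 depending on inputs the documents do not give.

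**Step 5. What each half of a remedy does.** A person-time denominator removes the effect of unequal length when the event rate is constant. It does not stop a subject's rate from blending on-treatment and off-treatment time if those rates differ; a common window does that. Both are needed.

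**The case against.** **The SAP sentence is about collection.** This is correct. A reader might infer that the SAP plans to analyse resource use through long-term follow-up, or that the counts will in fact mix windows. The text does not say so. It sets no analysis window, and restricting the data to the treatment-emergent period would remove the mixing. What stands is that no such restriction is written in SAP 4.11.4 or protocol 11.9. The aim appears only in the Amendment 8 log.

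**The mismatch is version lag, and the SAP already defines a treatment-emergent period.** Both are true. However, SAP 4.11.4 does not invoke the definition in SAP 4.2.1. That definition also stops the day before subsequent antineoplastic therapy, which the protocol's resource-use window does not.

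**A bias by arm is not shown.** Also correct. A reader might infer that the arm with more early stopping will look costlier. The documents give no Part 2 treatment durations or discontinuation times by arm, and the amendments applied to both arms alike.

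A tempting example assumes 0.8 hospitalizations per year in both groups. One group has 0.6 years on drug plus 1.0 year of follow-up, giving 0.8 × 1.6 = 1.28. The other has 1.0 year on drug only, giving 0.80, so the first is 60% higher. With the same inputs, the protocol window alone gives 0.8 × 0.6 = 0.48 against 0.80, a ratio of 0.80/0.48 = 1.67 in the opposite direction. A rate per patient-year returns 0.8 for both groups under either window. The missing denominator drives the example, not the mismatch between documents. The full year of follow-up also ignores the Amendment 7 stop at subsequent therapy.

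**An on-treatment window is not clearly best for economics.** A fixed period from randomization could be preferred in principle. The protocol no longer collects the data it would need for subjects who stop early.

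**Conclusion.** The inconsistency between SAP 4.11.4 and protocol 9.7 and Table 3 is real, and neither document closes it with a cut-off or a denominator. Taken as written, counts of hospitalizations and visits can cover unequal time across subjects, and possibly across arms. Post-treatment records can exist only for some of those who stopped before Amendment 8, and under the Amendment 7 rule only until subsequent therapy.

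The size and direction by arm cannot be determined from the documents. The 1.49 for a single window and the range 0.79 to 1.27 for mixed windows are illustrations. They rest on equal event rates, cycle counts taken from outside Part 2, and assumed follow-up shares and length.

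The consequence is limited. The endpoint is descriptive and is not among the secondary hypotheses tested under SAP 4.9.1.3. The primary result and type I error are unaffected. The point is worth correcting because the endpoint is a listed secondary one and the correction is cheap.

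**What to change.** In SAP 4.11.4:

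1. Replace the collection sentence with the window in protocol 9.7, and state that this window, rather than the general treatment-emergent period in SAP 4.2.1, governs resource use.
2. Apply that window (first dose to the later of the EOT visit and last dose + 30 days) to every subject in the by-arm summary, regardless of when or under which amendment the records were collected. Keep later encounters in listings only.
3. Report hospitalizations, hospital days, emergency visits and specialist visits per patient-year in that window, by arm, with 95% confidence intervals that allow for repeat events within a subject. Show the person-time beside each rate.

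A matching line in protocol 11.9 would keep the two documents together.

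The cost is SAP wording, a date filter and a denominator. Some post-treatment records already collected drop out of the comparison. The result is an on-treatment comparison and should be labelled as such, because its length depends on how long each subject stayed on drug.
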